8.2 Visit 2: First Interim (Week 4; Day 28 [redacted] Days)

The following procedures will be performed at Visit 2:

1. **Initial Check:** Temperature check and COVID-19 symptom screening.
2. **Pregnancy Test:** A urine pregnancy test will be conducted for all females of childbearing potential.
3. **Subject Compliance:** The Subject's compliance with the study protocol, including use, application and compliance of IMP, will be assessed. The Subject's diary will be collected and reviewed for completion.
4. **Investigational Medicinal Product:** The Subject's IMP dispensed at Visit 1 will be returned to the Independent Dispenser for review and re-dispensed if IMP remains.
5. **Concomitant Medication:** The use of concomitant medications since the previous study visit will be documented and assessed for each Subject.
6. **Adverse Events:** The occurrence of all AEs will be assessed and documented following procedures.
7. **Investigator Global Assessment:** The overall status of the Subject's facial acne vulgaris (from the jaw line to the hairline) will be assessed using the IGA by the Investigator or qualified staff member.
8. **Lesion Count:** Lesion counts will be done by counting the number of facial open and closed comedones, pustules, papules and nodulo-cystic lesions from the jaw line to the hairline. All lesions will be counted, including those present on the nose.
9. **Application Site Reaction:** Subjects will be evaluated for any signs and symptoms such as erythema, dryness, burning/stinging, erosion, edema, pain and itching.

10. Investigational Medicinal Product and Supplies:

The following will be dispensed during Visit 2:

- The investigational product (1 pump) (new pump assigned through the randomization system and or pump from screening/baseline visit re-dispensed if sufficient IMP remains)

- [redacted]
- [redacted]
- [redacted]

It is not anticipated that Subjects will require additional supplies during this visit; additional supplies will be dispensed if required.

- 
-
11. Study instructions will be reviewed with the Subject, including the procedure for application of the IMP.
 12. **Visit 3** (Day 56  days from the date of Visit 1): will be scheduled and the Subject will be instructed to bring all IMP (used, unused, and partially used) and the Subject diary with him or her to this visit. Subjects will be reminded not to use any facial topical products within 12 hours prior to the next scheduled clinic visit.

8.3 Visit 3: Second Interim (Week 8; Day 56 Days)

The following procedures will be performed at Visit 3:

1. **Initial Check:** Temperature check and COVID-19 symptom screening.
2. **Pregnancy Test:** A urine pregnancy test will be conducted for all females of childbearing potential.
3. **Subject Compliance:** The Subject's compliance with the study protocol, including use, application and compliance of IMP, will be assessed. The Subject's diary will be collected and reviewed for completion.
4. **Investigational Medicinal Product:** The Subject's IMP dispensed at the previous visit(s) will be returned to the Independent Dispenser for review, collection and or re-dispensed if IMP remains.
5. **Concomitant Medication:** The use of concomitant medications since the previous study visit will be documented and assessed for each Subject.
6. **Adverse Events:** The occurrence of all AEs will be assessed and documented following procedures.
7. **Investigator Global Assessment:** The overall status of the Subject's facial acne vulgaris (from the jaw line to the hairline) will be assessed using the IGA.
8. **Lesion Count:** Lesion counts will be done by counting the number of facial open and closed comedones, pustules, papules and nodulo-cystic lesions from the jaw line to the hairline. All lesions will be counted, including those present on the nose.
9. **Application Site Reaction:** Subjects will be evaluated for any signs and symptoms of signs and symptoms of facial irritation such as erythema, dryness, burning/stinging, erosion, edema, pain and itching.

10. Investigational Medicinal Product:

The following will be dispensed during Visit 3:

- The investigational product (1 pump) (new pump assigned through the randomization system if required and or pump dispensed at Visit 2 re-dispensed if IMP still remains).
- 

[REDACTED]

[REDACTED]

[REDACTED]

[REDACTED]

It is not anticipated that Subjects will require additional supplies during this visit; additional supplies will be dispensed if required.

11. Study instructions will be reviewed with the Subject, including the procedure for application of the IMP.
12. **Visit 4** (Day 84 [REDACTED] days from the date of Visit 1): will be scheduled and the Subject will be instructed to bring all IMP (used, unused, and partially used) and the Subject diary with him or her to this visit. Subjects will be reminded not to use any facial topical products within 12 hours prior to the next scheduled clinic visit.

8.4 Visit 4: End of Treatment (Week 12; Day 84 [REDACTED] Days)

The following procedures will be performed at Visit 4:

1. **Initial Check:** Temperature check and COVID-19 symptom screening.
2. **Pregnancy Test:** A urine pregnancy test will be conducted for all females of childbearing potential.
3. **Subject Compliance:** The Subject's compliance with the study protocol, including use, application and compliance of IMP, will be assessed. The Subject's diary will be collected and reviewed for completion.
4. **Investigational Medicinal Product:** The Subject's IMP dispensed at the previous visit(s) will be returned to the Independent Dispenser.
5. **Concomitant Medication:** The use of concomitant medications since the previous study visit will be documented and assessed for each Subject.
6. **Adverse Events:** The occurrence of all AEs will be assessed and documented following procedures.
7. **Investigator Global Assessment:** The overall status of the Subject's facial acne vulgaris (from the jaw line to the hairline) will be assessed using the IGA.
8. **Lesion Count:** Lesion counts will be done by counting the number of facial open and closed comedones, pustules, papules and nodulo-cystic lesions from the jaw line to the hairline. All lesions will be counted, including those present on the nose.
9. **Physical Examination:** A brief physical examination, including height (measured in inches) and weight (measured in pounds), will be performed. At a minimum, the physical examination will include the following: assessment of general appearance, skin, Head,

Eyes, Ears, Nose and Throat (HEENT), heart, lungs, musculoskeletal system, lymph nodes, neurological systems, abdomen, and extremities.

10. **Application Site Reaction:** Subjects will be evaluated for any signs and symptoms of erythema, dryness, burning/stinging, erosion, edema, pain and itching.

8.5 Unscheduled Visits and Early Discontinuation Visit

An Unscheduled Visit is allowed at any time, for any reason, if in the Principal Investigator's opinion, it is warranted. If the Unscheduled Visit is due to an AE, the Principal Investigator will determine whether additional visits are needed.

If a Subject is discontinued from the study during an Unscheduled Visit, the Unscheduled Visit will be referred to as an Early Discontinuation Visit and all procedures scheduled for the Early Discontinuation Visit will be performed. If the Unscheduled Visit is not an Early Discontinuation Visit (i.e., the Subject will continue to take part in the study), then the reason for the unscheduled visit is documented and required procedures at the discretion of Investigator considering the reason for visit will be performed apart from the collection of IMP and Subject diaries from Subjects.

If the Subject's condition has worsened to the degree that it is unsafe for the Subject to continue in the study, the Subject may be discontinued from the study as treatment failure and a standard of care treatment may be advised at the Principal Investigator's discretion.

[figure not shown]
8.6 Premature Termination of Study/Study Site

The Sponsor reserves the right to discontinue the study at any time. The reasons will be discussed with the Investigator. A study site may also be discontinued by the Sponsor for significant deviations from the protocol or due to difficulties experienced in running the study at that center.

The Sponsor may terminate this study in one particular or several study center(s) for one (or other) of the following reasons:

- a. Non-compliance with GCP and/or regulatory requirements
- b. Centre cannot recruit an adequate number of subjects
- c. False data captured in the eCRF due to carelessness or deliberately
- d. Inadequate co-operation with the Sponsor or its representatives
- e. The Investigator requests closure of his/her study center.

If the study is prematurely terminated in one or more study centers, all Investigators have to inform their subjects and take care of appropriate follow-up and further treatment of the subjects. Ethics Committees and regulatory authorities will be informed about the reason and time of termination according to the applicable laws and regulations.

The CRO should inform Teva Pharmacovigilance if the whole study is early discontinued due to safety reasons and should provide Teva Pharmacovigilance with the Early Termination Report.

8.7 Early Termination of a Subject

A subject may terminate from the study early for any reason at any time without any disadvantages. In this case, the Investigator should make every effort to have the subject return to the next scheduled visit to perform all required Early Termination (Early Discontinuation) visit activities and to collect and reconcile all study IMP. If the subject does not return for the Early Termination (Early Discontinuation) visit, the site should fully document the reason for early termination. All data, including the date and primary reason for termination, must be recorded on the Early Termination (Early Discontinuation) case report form (CRF), and source document.

Any subject who experiences an adverse event may be terminated from the study or from study treatment at any time at the discretion of the Investigator. In this case, the subject should be followed at the discretion of the Investigator until the resolution or stabilization of the AE. All applicable data should be recorded in the adverse events section of the case report form (CRF). If a subject terminates from the study early for multiple reasons that include adverse events, the Early Termination (Early Discontinuation) case report form should indicate that early termination was related to an adverse event.

An exception to this requirement will be the occurrence of an adverse event that in the opinion of the investigator is not severe enough to warrant early termination but that requires the use of a prohibited medication, thereby requiring discontinuation of the subject. In such a case, the reason for discontinuation would be needed to take a prohibited medication, not the adverse event.

The Investigator must inform the Medical Monitor and CRO as soon as possible of all subjects who are being considered for early termination due to adverse events. Additional reports must be provided when requested. The CRO will inform the Sponsor of this event.

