- 10) Subjects who have had facial cosmetic procedures (e.g., facials) or application of cosmetic products (cosmetics, makeup or facial products that have a strong drying or possible interactive effect, particularly preparations containing spices, lime sulfur, resorcinol, or salicylic acid with tretinoin or other retinoids) which may affect the efficacy and safety profile of the IMP within 2 weeks prior to study entry.

-
- 11) Subjects who have received radiation therapy and/or anti-neoplastic agents within 3 months prior to screening/baseline.
 - 12) Subjects who have used for less than (<) 3 months prior to screening/baseline estrogens or oral contraceptives; use of such therapy must remain constant throughout the study.
 - 13) Subjects who have used any of the following procedures on the face within 1 month prior to screening/baseline or use during the study:
 - a. cryodestruction or chemodestruction,
 - b. dermabrasion,
 - c. photodynamic therapy,
 - d. acne surgery,
 - e. intralesional steroids, or
 - f. X-ray therapy.
 - 14) Subjects who have used any of the following treatments within 1 month prior to screening/baseline or during the study:
 - a. androgen receptor blockers (e.g., spironolactone, Flutamide etc.)
 - b. systemic steroids,
 - c. systemic antibiotics,
 - d. systemic treatment for acne vulgaris (other than oral retinoids, which require a 6-month washout),
 - e. systemic anti-inflammatory agents. If Subject uses a systemic anti-inflammatory product during the study, the Principal Investigator will judge if this protocol deviation is clinically significant,
 - f. have taken any drugs that lower the immune system
 - g. topical immunomodulators
 - 15) Subjects who have used any of the following treatments within 2 weeks prior to screening/baseline or during the study:
 - a) topical steroids,
 - b) topical retinoids,
 - c) topical acne treatments including over-the-counter preparations
 - d) topical anti-inflammatory agents
 - e) topical antibiotics
 - f) abrasants,
 - g) peels containing glycolic or other acids,

-
- h) washes or soaps, containing glycolic acid,
 - i) Alpha-hydroxy acids,
 - j) sulfacetamide sodium,
 - k) non-mild facial cleansers, moisturizers that contained retinol
 - l) topical products that contain high amounts of alcohol
 - m) wax depilation of the face
 - n) use of tanning booths

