6.3 Evaluation of Signs/Symptoms of Local Irritation/Application Site Reactions

At each study visit, beginning at Visit 1, Subjects will be evaluated for any signs and symptoms of local irritation such as erythema, dryness, burning/stinging, erosion, edema, pain and itching. The scores for each visit will be documented to allow a comparison between treatment groups.

The following scale will be used for the signs and symptoms of local irritation:

Score	Assessment	Description
0	Absent	None
1	Mild	Slight, barely perceptible
2	Moderate	Distinct presence
3	Severe	Marked, intense

Subjects with a screening/baseline irritation score of 3 (severe, marked/intense) will not be enrolled.

Signs and symptoms of local irritation are to be recorded only as AEs if they significantly worsen, require any medical intervention or result in subject discontinuation (eg. after screening/baseline, severe irritation (i.e., grade 3, described as severe or marked/intense) that requires treatment will be reported as an adverse event).

Local irritation reactions in the treatment area are common and the Investigator may instruct Subjects to stop the application of treatment (“rest period”) to reduce Subject discomfort and to allow local skin reactions to subside based upon the Investigator’s clinical assessment. The Investigator may advise the subject to use the Sponsor provided moisturizer at this time. Treatment should resume as soon as the reaction subsides sufficiently to allow reapplication. The [REDACTED]. The Subject should not modify or resume the treatment regimen without consultation with the Investigator. The Investigator may make this decision based upon a documented phone consultation or at an unscheduled visit. All dose modifications must be reported on the appropriate Study Medication Log & Dosing Compliance eCRF, along with Subject documenting in the subject diary.

The treatment period should not be extended beyond 12 weeks due to missed doses or rest periods. Subjects whose condition worsens or lesions do not respond to treatment following at least 28 days (or in the opinion of the Investigator) should be re-evaluated by the Investigator and management reconsidered.

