7.2 Subject Disposition

The number of subjects enrolled in the study, randomized to treatment, included in the Safety, mITT and PP populations, prematurely discontinued from the study (along with the reasons for discontinuation) will be calculated. The percentages will be based on the number of subjects randomized to each treatment group. Percentages for discontinuation reasons will be based on the sub-population of subjects who discontinued from the study.

Number and percentage of subjects enrolled by site will be tabulated for all enrolled subjects, Safety, mITT, and PP populations.

Number and percentage of subjects excluded from each of the study populations will be summarized by reason for exclusion.

Details of subject eligibility, informed consent and disposition will be listed.

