7.7 Safety Analyses

7.7.1 Adverse Events

Adverse Events will be coded using the MedDRA version 25.0 AE coding system for purposes of summarization.

Only treatment-emergent adverse events (TEAEs) will be used for the summary analysis. An AE will be considered as treatment-emergent if the date of onset is on or after the date of the first study medication administration or if it increased in severity during the study treatment period. AEs with unknown start dates will be counted as treatment-emergent unless the AE resolution date is prior to the study drug start date. If the AE start date is partially missing, the

AE will be considered treatment-emergent, unless the month and year (when available) rule out the possibility that the event occurred post start of the study drug.

AE will be considered treatment-related if its relationship to study product is recorded as Possible, Probable or Definitely related. AEs with missing relationship will also be considered related.

An overall summary will include, by treatment group and overall, the number of TEAEs and the number and percentage of subjects reporting at least 1 TEAE in the following categories:

- Any AE
- Any TEAE,
- Treatment-related TEAE,
- Serious TEAE,
- TEAE leading to discontinuation of the study medication.
- Fatal AE

Count of AEs by severity and relationship to the study medication will also be presented.

The following TEAE frequency tables will be prepared summarizing the number and percentage of subjects reporting at least one TEAE by MedDRA system organ class (SOC) and preferred term (PT):

- All TEAEs
- Treatment-related TEAEs
- Serious TEAEs
- TEAE leading to discontinuation of the study medication
- TEAEs by maximum severity

A subject experiencing the same AE multiple times will only be counted once for that preferred term. Similarly, if a subject experiences multiple AEs within the same system organ class, that subject will be counted only once in that system organ class. In the summary by severity only the highest applicable severity will be chosen for each preferred term and system organ class.

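### Protocol 8.7 has some withdrawals caused by an adverse event recorded as prohibited-medication withdrawals, and SAP 7.7.1 does not say which record its discontinuation table uses

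*Protocol*

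**What the plan says.** Protocol 8.7 starts from a default. When a subject leaves for several reasons and one of them is an AE, the Early Termination form "should indicate that early termination was related to an adverse event". The next paragraph makes an exception for an AE that, in the investigator's opinion, "is not severe enough to warrant early termination but that requires the use of a prohibited medication". The coding is then reversed: "In such a case, the reason for discontinuation would be needed to take a prohibited medication, not the adverse event".

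Protocol 6.3 governs when local irritation counts as an AE. Signs and symptoms "are to be recorded only as AEs if they significantly worsen, require any medical intervention or result in subject discontinuation", and its example is severe irritation "that requires treatment will be reported as an adverse event". Exclusion criterion 15 in Protocol 5.1.2, headed "Subjects who have used any of the following treatments within 2 weeks prior to screening/baseline or during the study", lists topical steroids and topical anti-inflammatory agents.

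Two planned outputs count discontinuations. SAP 7.2 covers subjects "prematurely discontinued from the study (along with the reasons for discontinuation) will be calculated". SAP 7.7.1 has a separate category, "TEAE leading to discontinuation of the study medication", both in the overall summary and by system organ class and preferred term. The SAP does not say which data field defines that category.

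**The concern.** In the excepted cases the AE creates the need for the medication, and the medication need ends participation. The form records the second step and drops the first. This goes against the default one paragraph earlier, under which an AE among the reasons is enough for the AE to be shown.

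Which rule applies depends on the investigator's view of whether the AE alone would have justified stopping. That view can differ between sites, so similar cases can be coded differently.

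Protocol section 2 lists comparison of the safety of Test, Reference and Placebo as an objective, and the synopsis wants Test and Reference to be similar in application site reactions. A reader judging tolerability will look at how many subjects in each arm stopped because of an AE. The exception lowers that number for a defined subset.

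**Working it through.** No figure in the plan can be reproduced here: the documents give no rate of AE withdrawal, irritation or prohibited-medication use, and the sample size is redacted. The check is of the text, with one line of algebra.

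1. **Who is recoded.** Both conditions must hold: the AE is judged insufficient to warrant termination, and it needs a prohibited medication. An AE that does warrant termination is still coded as AE. So is a subject who wants to stop, or whom the investigator stops, because of an AE (Protocol 5.1.5 item g).

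2. **Whether the route is open in this trial.** Irritation that needs medical intervention is an AE (6.3). Topical steroids and topical anti-inflammatory agents are barred during the study (5.1.2, criterion 15 a and d). Irritation treated with one of these can therefore meet both conditions. Section 8.7 does not mention irritation; the exception covers any AE.

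3. **Disposition table (SAP 7.2).** Percentages for reasons use discontinued subjects as the denominator. In one arm let D be the number discontinued, A the number recorded with AE as reason, and k the number recoded under the exception.
   - Recorded AE share: A/D
   - Share by cause: (A + k)/D
   - Shortfall: (A + k)/D − A/D = k/D
   - Error in the Test minus Reference contrast of these shares (cause-based minus recorded): k_T/D_T − k_R/D_R

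   The shortfall is never negative. The contrast is distorted only if k/D differs between arms. None of k, A and D can be obtained from the documents.

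4. **AE table (SAP 7.7.1).** There are two possible sources. Protocol 11.1 has the action taken with study drug recorded for each AE, and SAP 7.7.1 lists it. If the table uses that field and the site records that drug was stopped for the event, nothing is lost, but this table and the disposition table can then disagree with no planned explanation. If it uses the termination reason, the same k subjects are missing here too.

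5. **What is unaffected among safety outputs.** The events remain in the tables of all, treatment-related and maximum-severity treatment-emergent AEs, in the Fisher comparison of Test with Reference for preferred terms above 1% in either group, and in the AE listing. Irritation scores are tabulated separately (SAP 7.7.4), although the shift table covers scheduled visits only, so a score taken only at an Early Discontinuation Visit may not appear in it.

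6. **Efficacy.** In SAP 7.6.2, last observation carried forward in the mITT analysis does not depend on the reason for leaving. In the per-protocol analysis the visible text gives special treatment only to lack of treatment effect; part of that sentence is redacted. As far as can be read, moving a subject between the AE and prohibited-medication codes changes neither analysis.

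7. **A related inconsistency.** Protocol 5.1.3 leaves it to the investigator whether a subject who breaks the restrictions is dropped. Protocol 8.7 treats discontinuation as the necessary result of needing a prohibited medication. Section 5.1.5 item j, on required therapy liable to interfere with the results, is also a listed ground for stopping. The size of k depends on which is followed.

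**The case against.** The exception is explicit, was set in advance and matches a listed ground for withdrawal (5.1.5 item j). Investigators are blinded, so it is applied alike in every arm. The subjects are relabelled and not removed: they still appear by arm under their own reason. The AE tables, the listing, the irritation scores and the concomitant-medication summary give several other views of the same events. On this account the choice is between two coding conventions, and no primary result moves.

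Most of this stands and limits the size of the point. Two parts do not dispose of it. Blinding makes the rule the same across arms, but not k: if one arm has more qualifying AEs, it has more subjects recoded. And a stated convention that contradicts the default beside it still leaves a table that does not count what its label suggests.

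A reader might go further and infer that irritation-driven withdrawals vanish from the AE discontinuation count, or that irritation treated with a prohibited topical is the typical AE withdrawal for this product. The documents support neither. Only the subset in step 1 is recoded, and whether the SAP 7.7.1 count is touched is open. On frequency, Protocol 6.3 describes a different course for irritation: a rest period, the sponsor's moisturizer and then resumption, with non-medicated moisturizer permitted in 5.1.3. No section says that prohibited topicals are the usual treatment.

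**Conclusion.** The point holds in a limited form and is minor. For AEs judged insufficient for termination but needing a prohibited medication, the SAP 7.2 table understates AE-caused discontinuations by k/D of the discontinued subjects in each arm. The SAP 7.7.1 table does so as well only if it is derived from the termination reason, which is unspecified. The value of k is unknown and could be zero. No bias between Test and Reference is shown; it would require k/D to differ between them.

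The conclusion assumes that sites follow 8.7 as written and that SAP 7.2 tabulates the reason on the Early Termination form. It is worth correcting because the count otherwise rests on a site-level opinion in a trial that compares safety across arms, and because the correction is cheap.

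**What to change.** - **Protocol 8.7:** remove the exception for recording purposes. Where a prohibited medication is needed to treat an AE and the subject leaves, record the AE as primary reason and the required prohibited medication as secondary. Say that this does not displace SAP 6.3, where worsening acne that needs rescue therapy is coded as lack of treatment effect, because that code decides per-protocol membership.
- **SAP 7.7.1:** derive treatment-emergent AEs leading to discontinuation from the AE record (action taken with study drug), and include withdrawals where a prohibited medication was needed to treat an AE. The link can be made from data already planned: the treatment given for each AE (Protocol 11.1) and the reason for each concomitant medication (Protocol 6.2 and 10.4).
- **Protocol 5.1.3, 5.1.5 item j and 8.7:** reconcile them on whether discontinuation is discretionary or required. Which rule should apply is a clinical decision for the sponsor.

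The recording and derivation changes cost one protocol sentence, matching text in the eCRF completion guideline and one derivation rule, to be settled before unblinding. They alter the recorded reason only, not anyone's treatment or who is withdrawn. Reconciling the discretion wording is a further short text edit.
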